The goal of the present study is to investigate the physiological effect of natural macronutrients when delivered exogenously to the proximal and distal small bowel. This will mimic some aspects of the physiological changes after Roux-en-Y gastric bypass. The oral administration of macronutrients in a protective capsule will enable us to deliver them to the proximal or the distal part of the small intestine depending on the chemical and physical properties of the capsules. Our study will provide important information on the physiological role of protein, fat, and carbohydrate content of the ingested food on specific gut hormone secretion and their effects on satiety

3 Potential side effects and risks

Blood sampling can cause mild pain and/or bruising. A doctor or a trained phlebotomist will insert this with experience in obtaining blood samples to minimise the discomfort caused. We do not expect any severe side effects

4 Study hypothesis

The delivery of high protein supplement to the proximal and distal gut will increase the release of anorexigenic gut hormones that have powerful satiety effect and will reduce food intake.

5 Study Objectives and Design

5.1 Primary Aim:

To identify the physiological satiety gut hormone response and the satiety response of subjects when macronutrients are digested in the distal rather than proximal small bowel.

5.1.1 Objective 1:

To quantify the physiological gut hormones response of differential macronutrient delivery to the proximal and distal small bowel.

5.1.2 Objective 2:

To quantify the physiological satiety response of differential macronutrient delivery to the proximal and distal small bowel.

5.1.3 Objective 3:

To quantify the amount of food consumed after a preload of differential macronutrient delivery to the proximal and distal small bowel.

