5.2 Study design

This is a randomized six-way crossover study. The study will include 10 healthy volunteers with each subject being studied on six separate occasions at weekly intervals (Figure 3).

[figure not shown]

Figure 3: Schematic of Study Design

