5.3 Primary endpoint

Changes in appetite as measured by visual analogue scale

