5.5 Study subjects

10 healthy volunteers of both sexes age 18 to 65 years will be recruited. Power analysis with amount energy ingested *ad lib* as endpoint indicate need for n=10 at power 80% and alpha of 0.05.

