5.5.3 Study procedures

At the screening visit a doctor or nurse will then perform the following tests and procedures to determine if the subject is eligible for the study:

- Medical history
- Physical examination
- Body measurements including height, weight and waist circumference
- Record of your medications or illnesses
- Urine pregnancy test (if applicable)

Visit 1-6 (1 week apart):

Subjects will be randomised to consume a one the 6 microcapsules in each week. Internet-based randomisation software will be used to allocate microcapsules to each subject at each visit

Eligible subjects will be invited to six consecutive visits in the clinical research centre at St Vincent University Hospital. On each occasion we would request you to have identical meals the night before between 19:00 and 20:00 hours and fast thereafter. Please refrain from alcohol and strenuous exercise for 24 hours before each study visit.

1. Food intake for the 24 h before each study day should be similar.
2. Participants will be asked to consume an identical meal between 19.00 and 20.00 on the night before each study (fish or pasta meal).
3. They will also be asked to be fasted and drink only water from 20.00 the night before the study.

In each visit, participants will be asked to be in the clinical research centre at 8:30. At 9:00 am a cannula will be inserted into the antecubital vein of the forearms. About 5 mL (1 teaspoon equivalent) will be taken to measure baseline hormone level. Another blood samples will be taken every 30 minutes thereafter. At 12:00, a final blood sample will be withdrawn and the cannula will be removed (total blood samples 7). They will be asked to answer a questionnaire regarding your feeling of hunger, satiety and if there is any nausea on a linear scale. Then a drink containing 200 grams of macronutrient microcapsules suspension equating to 1087 kcal will be offered. At 12:00 an *ad libitum* meal will be offered. After the meal they will also be provided with a similar questionnaire to fill in, in order to establish your fullness and satiety level. The total visit time is around five hours and there is a total of approximately 35 ml of blood (less than 2 table spoons) at each visit 1 to 6.

6 Methodology

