6.6.1 Blood samples processing

Serum will be separated immediately by centrifugation at 4°C and then stored at - 20°C freezer until analysis. GLP-1 and PYY assays will be performed on each sample.

7 Adverse event program

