Data will be analysed using GraphPad Prism (version 6.0) for Windows, GraphPad software (San Diego, CA, USA) and SPSS® (version 20.0) software (SPSS, Chicago, IL, USA). Central tendencies for patient and control group demographics, anthropometric data, caloric intake, VAS scores, QoL scores and macronutrient intake will be calculated and expressed using arithmetic mean \pm standard error of the mean or median (range), as appropriate. Differences in continuous variables between surgical and control groups will be calculated using the Student's *t* test or Mann-Whitney U test for parametric or non-parametric data, respectively. Correlative analyses will be performed using the Spearman Rho rank correlation to assess the relationship between *ad libitum* caloric intake and macronutrient intake with peri-operative weight loss and anthropometric data. Univariate analysis of factors associated with perioperative and post-surgical weight loss will be performed using Student's *t* test or one-way ANOVA for categorical variables or simple logistic regression for continuous variables. For the multivariate analysis, independent variables which were significant on univariate analysis, including standard demographic, oncologic and operative parameters as well as food intake and food preference, will be entered into a multiple logistic regression model with a forward stepwise selection procedure to assess their impact on perioperative and post-surgical weight loss. All statistical analyses will be two-tailed with the threshold of significance set at $P < 0.05$. Caloric intake and visual-analogue scores within groups will be compared by the Wilcoxon signed rank, matched-pairs test. Areas under the curve and plasma hormone levels will be compared by Wilcoxon rank-sum analysis.

12 Duration of Project

The estimated duration of the study will be 12 months. Screening and recruitment will begin in May 2017. Completion of the study is planned for May 2018.

13 Administrative considerations

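### Section 11 tests everything at two-sided 0.05 with six drinks to compare, no primary drink contrast and no multiplicity rule: about 14% to 40% false-positive risk on a single endpoint

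*Combined protocol and SAP*

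**What the plan says.** The design (section 5.2) is stated as "This is a randomized six-way crossover study". Section 1 lists the drinks: three macronutrient mixes, each in a stomach-release and a distal-release capsule. The primary aim (section 5.1) concerns the response "when macronutrients are digested in the distal rather than proximal small bowel". That gives a direction of interest, not a test.

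The primary endpoint (section 5.3) is "Changes in appetite as measured by visual analogue scale", with no item, time point or drink contrast. Gut hormones are secondary (section 5.4). The power statement (section 5.5) uses a different endpoint, ad libitum energy intake, and says calculations "indicate need for n=10 at power 80% and alpha of 0.05".

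On hormones, section 5.5.3 has a baseline sample and then "Another blood samples will be taken every 30 minutes thereafter", seven samples in all; section 6.6.1 adds "GLP-1 and PYY assays will be performed on each sample". One sentence of section 1 instead describes sampling only at the start and end of each visit.

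Section 11 assigns the paired signed-rank test to caloric intake and VAS scores, and the unpaired rank-sum test to hormone levels and areas under the curve. Its only error-rate rule is that "All statistical analyses will be two-tailed with the threshold of significance set at" 0.05. It does not mention the six drinks; its comparisons are worded for surgical and control groups.

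**The concern.** A threshold of 0.05 limits the false-positive risk of one test. Six drinks yield three matched location contrasts or 15 pairs for each endpoint, and the plan does not say which of these decides the question. If section 11 is followed literally, any contrast that crosses 0.05 on any outcome can be presented as support for distal delivery, and a reader cannot tell it from a pick among many. The plan labels no comparison exploratory. It states a hypothesis (section 4), and section 1 expects the results to inform food products, so a chance finding could be acted on.

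**Working it through.** **Plan's own figure.** The documents state no family-wise error rate. The one related figure is n = 10 at 80% power and alpha 0.05. It cannot be reproduced, because no effect size, SD or contrast is given. Solving backwards for a two-sided paired t test gives a standardised effect of 0.996, so about 1.0 SD of the within-subject difference is used below as an assumption.

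**Inputs from the documents.** n = 10; six drinks (3 macronutrients × 2 release sites); two-sided 0.05; signed-rank for VAS and intake; rank-sum for hormones; two hormones; seven samples, of which one precedes the drink and six follow it.

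**Number of comparisons per endpoint.** Matched distal versus stomach: 3. All pairs: 6 × 5 / 2 = 15.

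**Level of one signed-rank test at n = 10.** Rejecting when the smaller rank sum is 8 or less gives an exact two-sided level of 0.0488.

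**One endpoint, no true effect.**
- Three matched contrasts use disjoint pairs of drinks. If a subject's responses share only a common shift, that shift cancels in each difference and the contrasts are independent: 1 − (1 − 0.0488)³ = 0.139. Simulation (20,000 runs) gives 0.14.
- The 15 pairs share drinks and are correlated. Independence would give 1 − (1 − 0.0488)¹⁵ = 0.53, which is too high. Simulation gives 0.40.

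**Two endpoints, VAS and caloric intake.** With an assumed correlation of 0 to 0.7 between them, simulation gives 23–26% for 3 contrasts on each and 58–64% for 15 pairs on each.

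**Hormones, if levels were tested at every post-drink time.** 3 contrasts × 2 hormones × 6 times = 36 tests. Independence at 0.05 would give 1 − 0.95³⁶ = 0.84, an upper guide only. Simulation with assumed lag-one correlation over time of 0.5 to 0.9, and hormone correlation 0.3 for the rank-sum rows:

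| Test | Assumed within-subject correlation | At least one false positive |
|---|---|---|
| Rank-sum (as planned) | 0 | 54–76% |
| Rank-sum | 0.3 | 33–46% |
| Rank-sum | 0.5 | 16–25% |
| Rank-sum | 0.7 | 5–8% |
| Paired test (not planned for hormones) | any | about 57–81% |

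The rank-sum figures fall because an unpaired test on paired data leaves between-subject variation in its reference distribution. If each hormone is reduced to one AUC (3 × 2 = 6 tests), rank-sum gives 1–22% over the same settings.

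**Power cost of adjustment.** Paired t, n = 10, effect 1.0 SD: 80% at 0.05 and 60% at 0.05 / 3 = 0.0167.

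**The case against.** Five things can be said in favour of the plan.

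- **The aim is narrow.** It is distal against proximal, so the natural family is three matched contrasts. No objective asks for cross-pairs such as protein-stomach against fat-distal. This is fair: 14% is the figure for that reading on one endpoint. But section 11 does not restrict testing to it, and 14% is still nearly three times nominal.
- **Hormone testing at each time is inferred.** Section 11 names levels beside AUC without saying at which times, and levels could mean peak or end-of-visit values. This stands, so the 36-test family is conditional.
- **The planned hormone test is unpaired and conservative.** This also stands. A reader might infer that the hormone analyses alone make a false capsule effect more likely than not. Under the written test that needs a within-subject correlation near zero, and the 57–81% range belongs to paired tests that the plan does not assign to hormones.
- **Hormones are secondary in a ten-person physiology study.** True. Strict control over every secondary outcome is not required; labelling them exploratory would be enough.
- **The deeper fault is that section 11 is written for surgical and control groups.** That is a separate defect. It explains why no drink contrast was chosen but does not supply one.

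**Conclusion.** The point holds in a limited form. The plan has no primary drink contrast and no multiplicity rule, and following its single threshold gives about 14% (three matched contrasts) to 40% (all pairs) false-positive risk on one signed-rank endpoint. The risk is larger when VAS and intake are both tested. These figures assume no true effect and drink responses that are equally correlated within a subject.

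The documents do not support the stronger inference that a false positive is likely whatever is done. That holds only if all pairs are tested on both VAS and intake, or if hormones are tested at each time with a paired test or with little within-subject correlation. Nor do seven sampling times count towards a capsule effect, since the first sample precedes the drink. For three contrasts and two hormones at six times, the planned rank-sum test gives about 5–76%, and the correlation that decides where in that range the trial falls is not given.

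**What to change.** In section 11:

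1. Name one primary test: distal minus stomach release, averaged over the three macronutrients within each subject, at two-sided 0.05, on one prespecified VAS appetite measure and one time point (or an AUC). Without that choice several candidate primary tests remain. Sections 1 and 5.5.3 describe ratings only before the drink and around the test meal, so an AUC would need more rating times.
2. Test the three macronutrient-specific contrasts as a secondary family with Holm.
3. Summarise each hormone by one 0–180 minute AUC and compare it within subject instead of by rank-sum. Reconcile the two sampling descriptions so that this AUC is defined.
4. Report all other comparisons, including caloric intake and hormone levels at single times, as exploratory estimates with 95% confidence intervals.

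Items 1, 2 and 4 are wording, with no added subjects or visits unless an AUC is chosen for VAS. The specific contrasts lose power: at an assumed 1.0 SD, about 60% at the first Holm step against 80% unadjusted. Regaining 80% at 0.0167 would take about 14 subjects at the back-solved effect of 0.996. Averaging could also dilute an effect confined to the protein drink, on which the section 4 hypothesis rests: an effect δ there and none elsewhere averages to (δ + 0 + 0) / 3 = δ / 3. The specific contrasts would still report it. If the sponsor regards protein as the main question, the protein contrast could be made primary instead, provided it is chosen before the data are seen.

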Methods: Ten healthy volunteers, aged 18 to 65 years will be recruited. Each subject will be studied on six occasions one week apart. Prior to each study day, the subjects will consume an identical meal between 19.00 and 20.00 on the night before and refrain from alcohol and strenuous exercise for the 24 hours before and after each study day.

Subject will arrive to the Clinical Research Centre at St Vincent University Hospital at 08.30 having fasted the night before from 20.00. At 9:00 am a cannula will be inserted into the antecubital vein of the forearms. About 5 mL (1 teaspoon equivalent) will be taken to measure baseline hormone level. Another blood samples will be taken every 30 minutes thereafter. At 12:00, a final blood sample will be withdrawn and the cannula will be removed (total blood samples 7).

They will be asked to answer a questionnaire regarding your feeling of hunger, satiety and if there is any nausea on a linear scale. Then a drink containing 200 grams of macronutrient microcapsules suspension equating to 1087 kcal will be offered.

In a randomized way all subjects will receive a mixed meal containing 200 grams of macronutrient microcapsules suspension equating to 1087 kcal in their successive weekly visits:

- Option 1 High protein mixed meal in capsules that break down in the stomach,
- Option 2 High protein mixed meal in capsules that break down in the distal small bowel,
- Option 3 High fat mixed meal in capsules that break down in the stomach,

- Option 4 High fat mixed meal in capsules that break down in the distal small bowel,
- Option 5 High CHD mixed meal in capsules that break down in the stomach,
- Option 6 High CHD mixed meal in capsules that break down in the distal small bowel.

After 3 hours (i.e. at 12:00) participants will be offered standard *ad libitum* meal to measure their food consumption and another blood sample will be drawn. All subjects will be asked to rate their appetite on a Visual Analogue Scale (VAS) (see appendix B). Upon VAS completion the subjects will be allowed to go home.

Blood sample will be withdrawn from participants at the beginning and at the end of each visit. These samples will be used to quantify gut hormone levels

Conclusion:

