5.4 Secondary endpoints

Changes in gut hormone concentrations as indicated by serum levels of these hormones

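### Section 11 assigns the independent-samples rank-sum test to hormone levels and AUCs, although the same 10 volunteers supply every crossover condition

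*Combined protocol and SAP*

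**What the plan says.** Section 5.2 sets the design: "This is a randomized six-way crossover study". The Summary (Methods) gives all six drinks to all subjects in random order. They form three pairs, one per macronutrient, each with a stomach-release and a distal-release version; for instance "Option 2 High protein mixed meal in capsules that break down in the distal small bowel" is the partner of Option 1, the same type of meal released in the stomach. Section 5.5 gives a single group of 10 healthy volunteers.

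Gut hormones are the secondary endpoint (Section 5.4): "Changes in gut hormone concentrations as indicated by serum levels of these hormones". They are also Objective 1 (Section 5.1.1): "To quantify the physiological gut hormones response of differential macronutrient delivery to the proximal and distal small bowel". The primary aim (Section 5.1) covers the hormone and satiety responses "when macronutrients are digested in the distal rather than proximal small bowel".

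Section 11 then names two tests in consecutive sentences. For intake and VAS: "Caloric intake and visual-analogue scores within groups will be compared by the Wilcoxon signed rank, matched-pairs test". For hormones: "Areas under the curve and plasma hormone levels will be compared by Wilcoxon rank-sum analysis". No other section gives a method for comparing hormones between drinks.

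**The concern.** The rank-sum test (equivalent to Mann-Whitney U) treats the 10 values under one drink and the 10 values under another as coming from 20 unrelated people. Here they come from the same 10 people. The test therefore counts stable differences between volunteers as noise, whereas a paired test removes them.

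What is at stake is sensitivity. If a volunteer with high PYY or GLP-1 after one drink tends to be high after the others, the test rejects less often than its nominal level and can miss a real effect of distal release on the hormones that the trial's hypothesis is built on.

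**Working it through.** **The plan's own figure.** Section 5.5 states n=10 at 80% power and alpha 0.05, for *ad libitum* energy intake. It cannot be reproduced, because no effect size, SD, correlation or test is given. Solved backwards for a paired t-test (noncentral t, 9 df), n=10 corresponds to a standardised paired effect dz of about 1.00. The normal approximation gives (1.960 + 0.842)/√10 = 0.89. This concerns intake; no power was stated for hormones.

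**Mechanism.** Let each drink have SD σ and let ρ be the within-subject correlation.
- True variance of the mean difference in a crossover: 2σ²(1 − ρ)/n.
- Variance assumed by an independent-samples comparison: 2σ²/n.
- Ratio of assumed to true: 1/(1 − ρ), which is 1 at ρ = 0, 2 at ρ = 0.5 and 5 at ρ = 0.8.

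This is the argument for means; the rank tests behave in the same direction.

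**Inputs for the illustration.** From the documents: n = 10 per drink, same subjects (Sections 5.2, 5.5), two-sided 0.05 (Section 11). Assumed: bivariate normal data, one value per subject per drink (for example an AUC), one distal-stomach pair, ρ from 0 to 0.8.

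**Rejection rules.** Rank-sum, 10 versus 10: reject if the smaller U ≤ 23 (exact size 4.33% for independent samples). Signed-rank, 10 pairs: reject if the smaller W ≤ 8 (exact size 4.88%).

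**Results** (simulation; repeat runs agree within about one point):

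| Correlation | 0 | 0.3 | 0.5 | 0.7 | 0.8 |
|---|---|---|---|---|---|
| True size, rank-sum (%) | 4.2 | 1.9 | 0.8 | 0.2 | under 0.1 |
| Power at 1 SD, rank-sum (%) | 51 | 52 | 52 | 55 | 56 |
| Power at 1 SD, signed-rank (%) | 50 | 64 | 78 | 94 | 99 |
| Loss (points) | none | 12 | 26 | 39 | 43 |
| Power at 1.5 SD, rank-sum (%) | 85 | 89 | 91 | 94 | 96 |
| Power at 1.5 SD, signed-rank (%) | 83 | 93 | 98 | 100 | 100 |
| Loss (points) | none | 4 | 7 | 6 | 4 |

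The signed-rank test keeps a true size of about 4.9% throughout. For a 0.5 SD effect at correlation 0.5, power is 10% against 28%.

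**Cross-check on the other scale.** Fixing the paired effect at dz = 1.00 instead of the raw effect, signed-rank power stays at about 78%, and rank-sum power is 81/68/52/28/14% at the same five correlations. The raw effect equals dz·√(2(1 − ρ)), so the two scales coincide at ρ = 0.5, and both give 52% against 78% there.

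**The case against.** The strongest reply is that the sentence is carried over. Much of Section 11 describes a surgical-versus-control study with perioperative weight loss, quality-of-life scores and oncologic variables, and the signed-rank sentence speaks of comparisons within groups. The rank-sum sentence may be that study's between-group test, or a slip for signed-rank. A reader might infer from the paired test one sentence earlier that the authors deliberately chose an unpaired test for hormones; the surrounding text leaves that unproven. The origin does not rescue the sentence, however: this trial has no parallel groups, so no reading makes the test valid.

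The second reply is that the consequence is limited, and this stands. Only the secondary endpoint's test is affected, no hormone power was claimed, and for one value per subject per drink the error is conservative under positive correlation.

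Two stronger readings go beyond the documents. First, Section 11 does not say how the seven samples per visit (Section 5.5.3) enter the comparison of hormone levels. A reader might infer that 7 × 10 = 70 values per drink would be pooled, with false positives above 5%. The plan does not state that reading, the result would depend on variance shares that the documents do not give, and a post-meal time course common to both drinks reduces any inflation. The Summary also speaks of sampling only at the start and end of each visit, so even the count is not wholly consistent. Second, whether the main contrast averages over macronutrients or concerns protein alone is a separate question, which correcting the test would not settle.

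**Conclusion.** The point holds: the independence assumption of the only test named for comparing hormones between drinks is false by design, whatever the correlation. It should be fixed, and merits no higher grade than that.

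The practical loss depends on unknowns. On the assumptions above it ranges from nothing at correlation 0, through 4 to 7 points for a 1.5 SD effect at correlation 0.3 or more, to 26 to 43 points for a 1 SD effect at correlation 0.5 to 0.8. These figures illustrate direction and possible size; they do not predict this trial's power.

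A reader might infer that hormone findings from this plan would be unreliable in general. That does not follow. With one AUC per subject per drink and positive correlation, a significant result would survive this criticism; it is a non-significant result that would be hard to interpret. Nor does the point reach the primary endpoint, for which Section 11 already names a paired test.

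**What to change.** In Section 11, replace the rank-sum test for hormones with the matched-pairs signed-rank test already assigned to intake and VAS. State that it is applied to one summary per subject per visit (for example the AUC), on the distal-minus-stomach difference within each macronutrient: Option 2 minus 1, 4 minus 3, and 6 minus 5. Delete the surgical-versus-control and perioperative text as clean-up.

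The cost is two or three sentences. No extra subjects, samples or assays are needed.
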